### 9.7.3 *Other procedures*

#### **CGI**

The CGI consists of 2 sub-scales: CGI-S and CGI-I. Clinical Global Impression scale – Severity of illness (CGI-S) and Clinical Global Impression scale - Improvement (CGI-I) will be used to assess patient's overall severity and improvement/worsening of depression [60]. CGI-I of the current visit will be assessed compared to a CGI-I score of the last visit. CGI-S will be conducted at visit 1, 2, 3, 4, 5 and 6, whereas CGI-I will be conducted at visit 2, 3, 4, 5 and 6 by the subinvestigator.

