Hypotheses / endpoints	
Primary hypothesis:
 
Simvastatin (40 mg/d) add-on to standard antidepressant Escitalopram (20 mg/d) will improve depression to a greater extent than add-on placebo in patients with comorbid obesity and major depression
 
Primary efficacy (confirmatory) endpoint
 
Change score from baseline to week 12 in Montgomery-Asberg-Depression Rating Scale (MADRS)
 
Secondary Hypotheses:
 
Add-on Simvastatin (40 mg/d) to standard antidepressant Escitalopram (20 mg/d) will improve
 
 
1) response rates and remission rates
 
2) patients' impression of change, clinicians' impression of severity and improvement, quality of life, social functioning, self-report depression
 
3) lipid values
 
4) mitochondrial and cellular function of immune cells
 
 
to a greater extent over 12 weeks than adjunct placebo in patients with major depression and comorbid obesity.
 
Secondary efficacy (exploratory) endpoints
 
 
1) MADRS-response (50 % MADRS score reduction from baseline), MADRS-remission (MADRS score < 10), and MADRS-minimal clinically important difference (MCID)
 
2) change Beck Depression Inventory (BDI-II) scores from baseline to week 12, and BDI-II-MCID
 
 
Other secondary (exploratory) endpoints
 
 
2) change in Patients' Global Impression of Change Scale (PGIC), change in Clinicians' Global Impression of Severity of illness (CGI-S), Clinicians' Global Impression of Improvement (CGI-I), EuroQol-5 Dimensions-3 Levels Questionnaire (EQ-5D-3L), and Social and Occupational Functioning Assessment Scale (SOFAS) from baseline to week 12
 
3) change in high-density lipoprotein (HDL), low-density lipoprotein (LDL), and total cholesterol from baseline to week 12
 

	4) change in mitochondrial and cellular function of immune cells from baseline to week 12
Study design	multicenter, randomized, double-blind, placebo-controlled, parallel-group

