Hypothesen / Endpunkte	
Primäre Hypothese:
 
Simvastatin (40 mg/d) als Zusatztherapie zur konventionellen Antidepressiva-Standardtherapie mit Escitalopram (20 mg/d) führt zu einer zusätzlichen Verbesserung der Depression im Vergleich zu einer Zusatzbehandlung mit Placebo bei Patienten mit Major Depression und komorbider Adipositas
 
Primärer (konfirmatorischer) Endpunkt
 
Veränderungsscore von Baseline zur Woche 12 in der Montgomery-Asberg-Depression Rating Skala (MADRS)
 
Sekundäre Hypothesen:
 
Simvastatin (40 mg/d) als Zusatztherapie zur konventionellen Antidepressiva-Standardtherapie mit Escitalopram (20 mg/d) führt nach 12 Wochen zu einer zusätzlich verbesserten
 
 
1) Ansprech- und Remissionsrate
 
2) Veränderungseinschätzung durch Patienten, Schwere- und Veränderungseinschätzung durch Behandler, Lebensqualität, Sozialem Funktionsniveau, selbstberichtete Depression
 
3) Lipidwerte
 
4) Immunometabolismus / mitochondriale Funktion
 
 
im Vergleich zur Behandlung mit Placebo bei Patienten mit Major Depression und komorbider Adipositas
 
Sekundäre (explorative) Endpunkte (Effektivität)
 
 
1) Ansprechrate (Reduktion der Punkte im MADRS um 50 % zur Baseline), Remission (MADRS Punkte < 10) und MADRS geringster klinisch relevanter Unterschied (MCID)
 
2) Veränderung in den Beck Depression Inventory (BDI-II) Punkten von Baseline zu Woche 12 und geringster klinisch relevanter Unterschied (MCID)
 

	
Weitere sekundäre (explorative) Endpunkte
 
2) Veränderung in der Patients' Global Impression of Change Scale (PGIC), Veränderung in der Clinicians' Global Impression of Severity of illness (CGI-S), Clinicians' Global Impression of Improvement (CGI-I), EuroQol-5 Dimensions-3 Levels Questionnaire (EQ-5D-3L), Social and Occupational Functioning Assessment Scale (SOFAS) von Baseline zu Woche 12
 
3) Veränderung in high-density lipoprotein (HDL), low-density lipoprotein (LDL) und total Cholesterin von Baseline zu Woche 12
 
4) Veränderung in der respiratorischen Reserve von Monozyten und T Zellen und andere zelluläre Funktionen von Baseline zu Woche 12

Studiendesign	multizentrisch, randomisiert, doppel-blind, Placebo-kontrolliert, Parallelgruppen

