### 5.2.2 Other secondary (exploratory) endpoints

We will additionally determine

- The clinician's impression of the severity of illness (Clinical Global Impression scale – Severity of illness, CGI-S) [60],
- the clinician's impression whether and to what extent symptoms have improved (Clinical Global Impression scale – Improvement, CGI-I) [60],
- the patient's impression whether and to what extent symptoms have improved (Patients' Global Impression of Change Scale, PGIC),
- social functioning (Social and Occupational Functioning Assessment Scale, SOFAS),
- quality of life (EuroQol-5 Dimensions-3 Levels Questionnaire, with a calculated MCID [61]),
- change scores in high-density lipoprotein (HDL), low-density lipoprotein (LDL), and total cholesterol,
- and change scores in mitochondrial function (spare respiratory capacity) of immune cells and indicators of immune function.

Please see Table 1 for characteristics and definitions of primary and secondary outcome variables.

**Table 1:** Characteristics and definitions of primary and secondary endpoints.

Outcome	Instrument	Rating	Domain	Exactly defined outcome	Variable
Primary	MADRS	Clinician-rated	Severity of Depression	Mean Change from Baseline	Continuous

Secondary / Efficacy (exploratory)	MADRS	Clinician-rated	Severity of Depression	- Percentage response (>50 % reduction from baseline) - Percentage remission (MADRS score < 10 post-treatment) - Percentage minimal clinically important difference (MCID; change from baseline score > 1.9)	Dichotomous
Secondary / Efficacy (exploratory)	BDI-II	Self-rated	Severity of Depression	Mean Change from Baseline - Percentage MCID (> 17.5% change from baseline)	Continuous Dichotomous
Secondary Exploratory	CGI-S	Clinician-rated	Severity of illness	Median Change from Baseline	Ordinal
Secondary Exploratory	CGI-I	Clinician-rated	Improvement/worsening of illness	Response defined as "much improved" or "very much improved" post-treatment	Dichotomous
Secondary Exploratory	PGIC	Self-rated	Subjective Improvement	Response defined as "much improved" or "very much improved" post-treatment	Dichotomous
Secondary Exploratory	SOFAS	Clinician-rated	Social Functioning	Mean Change from Baseline	Continuous
Secondary Exploratory	EQ-5D-3L	Self-rated	Quality of Life	Mean Change from Baseline Percentage MCID (change from baseline score > 0.74)	Continuous Dichotomous
Secondary Exploratory	HDL, LDL, total cholesterol	Laboratory values	Metabolism	Mean Change from Baseline	Continuous

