Secondary Exploratory	Mitochondrial and cellular function of immune cells	Laboratory values	Immune function	Mean Change from Baseline	Continuous

The time point for the evaluation of the secondary endpoints is 12 weeks. The secondary efficacy endpoints MADRS-response and MADRS-remission within 12 weeks will be analyzed by logistic regression models with intervention and center as factors and baseline MADRS as covariate. The analyses of continuous secondary efficacy endpoint BDI-II, and continuous secondary exploratory endpoints SOFAS, and EQ-5D-3L will follow the same lines as the primary outcome. The analyses of safety parameters and all secondary endpoints will have an exploratory character.

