## 9.4 Visits schedule and evaluations

**Table 3: Overview and frequencies of trial examinations**

Assessments	Screening	Base-line (Visit 1)	Visit 2	Visit 3	Visit 4	Visit 5	End-of-study (Visit 6)
		week 0	week 1	week 2	week 4	week 8	week 12
Screening and consent							
Informed consent	X						
Inclusion criteria		X					
Exclusion criteria		X	X	X	X	X	X
Medical history	X						
Treatment status		X					
M.I.N.I – DSM 5	X						
Urine/serum drug screening	X						
Concomitant medication	X						
Safety							
Physical exam	X						X
ECG	X	X	X	X	X	X	X
Blood pressure & heart rate	X	X	X	X	X	X	X
Safety laboratory (incl. Pregnancy test - women only)	X	X			X	X	X
Adverse events recording			X	X	X	X	X
Effectiveness							
MADRS	X	X	X	X	X	X	X
BDI-II		X	X	X	X	X	X
Social functioning and quality of life							
SOFAS		X			X		X
EQ-5D-3L		X			X		X
Other							
Demographics	X						
BMI	X	X					X
Waist circumference		X					X
PGIC			X	X	X	X	X
CGI-S		X	X	X	X	X	X
CGI-I			X	X	X	X	X
Laboratory (lipid assessment)		X					X

Laboratory (immunometabolism / mitochondrial function)	X		X	X	X
Drug dispensation	X	X	X	X	

Note: Electrocardiography (ECG), Body-Mass-Index (BMI), Mini International Neuropsychiatric Interview (MINI), Montgomery-Asberg Depression Scale (MADRS), Beck-Depressions-Inventar (BDI), Patient Global Impression of Change (PGIC), Clinicians' Global Impression of Severity of illness (CGI-S), Clinicians' Global Impression of Improvement (CGI-I), Social and Occupational Functioning Assessment Scale (SOFAS), Generic Quality of Life Questionnaire (EQ-5D-3L).

Maximum variation of  $\pm 3$  days is permitted for the scheduling of each study visit.

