#### 16.1.2 *Secondary hypotheses*

[figure not shown]
Add-on Simvastatin (40 mg/d) to standard antidepressant Escitalopram (20 mg/d) will improve:

- 1) response rates, and remission rates,
- 2) patients' impression of change, clinician's impression of severity and change, quality of life, social functioning, self-report depression,
- 3) lipid values,
- 4) mitochondrial and cellular function of immune cells

to a greater extent over 12 weeks than adjunct placebo in patients with major depression and comorbid obesity.

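### Section 9.7.3 rates CGI-I against the previous visit, so the week-12 response describes change since week 8, not the baseline-to-week-12 outcome listed in the synopses

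*Combined protocol and SAP*

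**What the plan says.** Section 9.7.3 gives the rater one instruction on the reference point: "CGI-I of the current visit will be assessed compared to a CGI-I score of the last visit". The next sentence sets the visits: CGI-S starts at visit 1, "whereas CGI-I will be conducted at visit 2, 3, 4, 5 and 6 by the subinvestigator". No CGI-I is taken at baseline.

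The endpoint is described in four other places:

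- Section 1 (Synopsis, other secondary endpoints) lists "Clinicians' Global Impression of Improvement (CGI-I), EuroQol-5 Dimensions-3 Levels Questionnaire (EQ-5D-3L), and Social and Occupational Functioning Assessment Scale (SOFAS) from baseline to week 12". The same list in the German synopsis (section 2) ends "SOFAS) von Baseline zu Woche 12".
- Table 1 in section 5.2.2 defines the CGI-I outcome as "Response defined as 'much improved' or 'very much improved' post-treatment". It names no reference point.
- The text after Table 1 states: "The time point for the evaluation of the secondary endpoints is 12 weeks".
- Section 16.1.2 includes the clinician's impression of change among the outcomes expected to improve "to a greater extent over 12 weeks than adjunct placebo in patients with major depression and comorbid obesity".

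CGI-I has a second use. Section 11.1 discontinues a patient whose CGI-I is 6 or 7 (much worse or very much worse) at two successive visits.

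**The concern.** The rating procedure and the endpoint cover different intervals. An improvement scale has no meaning without its reference point, and here the rater is given the previous visit while the endpoint lists run from baseline. A patient who is much better by week 4 and stays well has no further change to report at week 12 against week 8, and so drops out of the responder count.

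Analysis cannot repair this afterwards. Section 16.4 leaves details to a later statistical analysis plan, but such a plan cannot change the reference that raters used. No section says how visit-to-visit ratings would be combined. Ordinal categories do not simply add up: two successive ratings of slight improvement do not settle whether the total amounts to much improved.

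The sentence also cannot be applied literally at visit 2, because there is no CGI-I score from visit 1 to compare with.

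**Working it through.** The plan states no figure on this point, so there is none to reproduce. The check has three parts.

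**1. The interval that the week-12 rating covers**

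Inputs: baseline is week 0, visit 5 is week 8 and visit 6 is week 12 (section 9.4, Table 3). The note to Table 3 says that a variation of at most ±3 "days is permitted for the scheduling of each study visit". I take baseline as day 0 and count the windows from it.

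- Visit 5: day 56 ± 3, so day 53 to 59. Visit 6: day 84 ± 3, so day 81 to 87.
- Nominal look-back: 84 − 56 = 28 days; 28/84 = 33%.
- Shortest: 81 − 59 = 22 days; 22/81 = 27%.
- Longest: 87 − 53 = 34 days; 34/87 = 39%.

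These figures describe the schedule. They are not a share of patients.

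**2. How the rule classifies single paths**

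One step is a change large enough to be rated much improved or much worse. No frequencies are assumed.

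| Path | Week 12 against baseline | Week 12 against week 8 |
|---|---|---|
| A. Improves one step by week 4, stays well | responder | non-responder |
| B. Worsens one step by week 8, recovers to baseline severity by week 12 | non-responder | responder |
| C. Unchanged to week 8, improves one step by week 12 | responder | responder |

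Path A removes true responders and path B adds false ones. The net change in the response rate depends on how common A and B are. The change in the difference between arms depends on how A and B are distributed over the two arms. The documents give neither.

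**3. The section 11.1 criterion**

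| Path | Reference is baseline | Reference is last visit |
|---|---|---|
| D. Much worse once, stays there | met | not met |
| E. Improves, relapses to baseline severity in one step, stays there | not met | not met |
| F. Improves two steps, then much worse at each of two successive visits, back to baseline severity | not met | met |

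Each reference catches a pattern that the other misses (D and F), and neither catches E.

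**The case against.** **Table 1 does not say baseline.** It writes change from baseline for CGI-S, SOFAS, EQ-5D-3L and the lipids, but only post-treatment for CGI-I. The baseline interval for CGI-I comes from a trailing phrase shared by a list in each synopsis. That phrase also covers PGIC, which is not taken at baseline, so the drafting is loose. This stands: the conflict is between section 9.7.3 and the synopses, and Table 1 leaves the reference open. It does not rescue the instruction, because no section describes an endpoint running from week 8 to week 12.

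**The sentence is awkward, and raters may use baseline anyway.** It compares a rating with a score rather than with the patient's condition, and it cites a scale manual that is not among the documents. How sites will actually rate is therefore unknown, and the misclassification is conditional on raters following the text. But the text is the only instruction they have. The training in section 9 is general, and the scale-specific training in section 9.5.1 concerns the MADRS. If some raters follow the sentence and others use baseline, the pooled endpoint mixes two measures.

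**The consequence is small.** This stands. Section 16.4 treats all secondary endpoints as exploratory, without adjustment for multiple testing, and names no model for CGI-I. MADRS response and CGI-S change still provide clinician-rated, baseline-referenced information.

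**Stronger readings that the documents do not support.** A reader might infer that the CGI-I response rate must come out too low, or that the treatment difference must shrink. Path B rules out certainty on the first. On the second, if one arm improves earlier, the slower arm may show more change between weeks 8 and 12. A loss of power could be calculated only by assuming response rates and shares of early responders in each arm, so none is given. A reader might also infer that the section 11.1 criterion is wrong; paths D and F show that it is a choice between two references.

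**Conclusion.** The point holds. Followed as written, the week-12 CGI-I rating describes the last 28 of 84 days (22 to 34 days within the visit windows) and does not measure the baseline-to-week-12 outcome in the synopses. It misclassifies patients in both directions. The size and sign of the net effect, on the response rate or on the comparison of arms, cannot be determined from the documents.

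This rests on reading the comparison with the last visit's score as a comparison with the patient's condition at that visit, which is the likely meaning, and on raters doing what section 9.7.3 says.

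The damage is limited to one exploratory secondary endpoint. The correction is worth making because a prespecified endpoint should be obtainable from its own rating procedure, and because it cannot be recovered once ratings have been taken.

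**What to change.** Replace the sentence in section 9.7.3 with: *CGI-I is rated relative to the patient's condition at baseline (visit 1).* This should apply at least to the visit 6 rating, which defines the endpoint. Remind raters. Table 1 can keep its week-12 response definition.

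Section 11.1 should state which reference its CGI-I criterion uses. That is the sponsor's choice:

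- **Baseline at all visits.** There is one consistent reference, and sustained worsening from baseline (path D) is caught. A stepwise relapse after improvement (path F) is no longer caught and would rest on the general best-interest clause of section 11.1.
- **Last visit for visits 2 to 5, baseline for visit 6.** If the reference is worded as the patient's condition at the last visit, the current discontinuation rule is kept for the visit pairs 2–3, 3–4 and 4–5. The pair 5–6 falls at end of study and cannot shorten treatment. The cost is that raters change reference at the final visit, and that ratings from visits 2 to 5 cannot show the course of response or stand in for a missing visit 6.

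Ratings already taken under the present instruction should be reported as change since the previous visit and not pooled into the baseline-referenced response. CGI-S change should not be substituted for them: it is a separate ordinal endpoint, and no rule converts it into a CGI-I response.

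The cost is one sentence in section 9.7.3, one clause in section 11.1 and a rater reminder. No visit or assessment is added.

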#### **SOFAS**

The Social and Occupational Functioning Assessment Scale (SOFAS) will be used to determine social functioning [76] and will be conducted at baseline, week 4 and end-of-study by the subinvestigator.

#### **BMI, measurement of waist circumference**

Body-Mass-Index will be determined by measuring weight at screening, baseline and end-of-study by study staff. Height will be measured only once at screening. Waist circumference will be measured at baseline and end-of-study by study staff.

## **10. Risk-benefit-assessment**

Both medications (Simvastatin, Escitalopram) are approved for several indications since decades and have overall been proven to be safe. All depressed patients enrolled in the trial will be continuously treated with a gold standard antidepressant (Escitalopram) as described by the National

Disease Management Guideline (“Nationale Versorgungsleitlinie”) for the treatment of MDD. For Escitalopram a dose-response relationship has been suggested. Especially for patients with severe depression the high standard dose of 20 mg/d was shown to be superior compared to 10mg/d [1]. A fixed-dose of 10 mg/d Escitalopram for the entire study duration of 12 weeks would therefore not allow the optimal treatment for some patients. Thus, we consider this option ethically not justifiable. A dose increase from 10 mg/d to 20 mg/d based on individual patient response would however interfere with comparability of the treatment group and placebo group, because a strong decrease in depressive symptoms in the treatment group compared to placebo group could potentially be masked by a higher percentage of Escitalopram dose escalation in the placebo group. Therefore, we will increase Escitalopram to 20 mg/d after giving a low standard dose of 10 mg/d in the first two weeks. In case of adverse reactions related to Escitalopram, we will follow the instructions for dose adjustment described in 7.2.4 Treatment schedule / Dose regimen.

IMP Simvastatin is offered in an “add-on” design, thus there will be virtually no drug-free patients in this trial. Invasive interventions beyond ordinary sampling of peripheral venous blood will not be performed within this trial, therefore the risks associated with trial participation are mainly attributable to IMP Simvastatin that has already been shown in depressed patients to be safe and well tolerated in combination with an SSRI.[2]

It has been suggested that both for the lipid-lowering effects and for the pleiotropic effects of statins a high dose is more effective than a low dose [3-5]. Especially in studies examining effects of statins on diseases of the central nervous system such as multiple sclerosis and mild cognitive disorder a high dose of Simvastatin (60 – 80 mg/d) has been administered [6-8]. One of the most important side effects of Simvastatin is dose-dependent risk of myopathy. The combined incidence for myopathy/rhabdomyolysis under Simvastatin was 0.03% for 20 mg/d, 0.08% for 40 mg/d and markedly went up to 0.61% for 80 mg/d according to latest version of German “Fachinformation”. To minimize the risk of Simvastatin and examine the pleiotropic effects of Simvastatin in depression, we will use it in a medium dose (40 mg/d) and not a high dose (80 mg/d). In addition to assessing safety laboratory values including creatine kinase (CK) at screening, baseline, at week 4, week 8 and week 12, it will be explicitly asked during each visit if the patient experienced unexplained muscle pain or dark urine as a sign of rhabdomyolysis. Furthermore, we will not include particularly vulnerable patients (e.g. patients with renal impairment, untreated hypothyroidism or history of muscle toxicity under statins or fibrates) to our study. To exclude patients with QTc-prolongation an ECG will be conducted at screening. Furthermore, additional safety ECGs will be conducted at every visit.

According to a meta-analysis of small, randomized controlled trials, a beneficial antidepressive effect of Simvastatin is to be expected [2]. Many depressed patients with comorbid obesity might additionally benefit from Simvastatin in terms of primary prevention of cardiovascular disease.

In summary, the potential benefits of the study by far outweigh the risks associated with Escitalopram and Simvastatin. Importantly, a recent extensive literature review on parallel SSRI and statin use concluded the following: “Escitalopram, Citalopram, and Paroxetine are almost certain to be safe with all statins” [9].

## **11. Termination and subsequent treatment**

### **11.1 Premature termination of the individual participant**

Patients are free to withdraw from participation in the study without specifying any reasons. An investigator may discontinue or withdraw a participant from the study for the following reasons:

- If any clinical adverse event (AE), laboratory abnormality, or other medical condition occurs

such that continued participation in the study would not be in the best interest of the participant. In particular the following AE, laboratory abnormality, or other medical condition will lead to immediate discontinuation of the individual participant:

- report of any unexplained muscle pain, tenderness or weakness if accompanied by malaise or fever
- hyperbilirubinemia or jaundice
- interstitial lung disease
- QTc prolongation  $\geq 500$  ms or  $\geq 60$  increase from baseline visit
- seizures
- activation of mania/hypomania
- abnormal bleeding event (e.g. ecchymoses, purpura)
- serotonin syndrome
- angle closure glaucoma
- clinically significant worsening of depression severity operationalized as a CGI-I change score of 6 or 7 (“much worse” or “very much worse”) in two successive visits.
- clinically significant laboratory abnormalities such as
  - elevated creatine kinase greater than 5fold upper limit of normal (ULN)
  - elevated GOT or GPT greater than 3fold upper limit of normal (ULN)
  - severe symptomatic hyponatremia (serum sodium [ $S_{Na}$ ]  $<125$  mmol/L)
  - elevated thyroid-stimulating hormone outside of the age- and sex-specific reference intervals
- acute suicidal ideation (MADRS item 10  $> 4$ )
- pregnancy

In the case of premature termination, the reason for withdrawal must be entered on the appropriate case report form (eCRF) page and the patient must be followed for safety and efficacy until the end of the study (week 12).

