### **9.6.2 Laboratory safety**

Safety laboratory will be performed at screening, baseline, visit 4, visit 5 and at the end-of-study. Components of the laboratory panels include tests for the following:

- Blood count (leukocytes, erythrocytes, hemoglobin, hematocrit, MCV, MCH, MCHC, RDW-CV, thrombocytes, MPV) and differential blood count (neutrophiles, granulocytes, lymphocytes, monocytes, eosinophiles, basophiles, neutrophiles)
- Clinical chemistry [sodium, potassium, creatinine, estimated GFR, GOT (AST), GPT (ALT), gamma-GT
- Creatine kinase (CK)
- CRP
- Basal glucose and HbA1c
- Beta-HCG (women only).

At screening visit thyroid-stimulating hormone (TSH) and Carbohydrate-deficient Transferrin (CDT) will be additionally determined.

Sample collection will take place at each investigator site by the subinvestigator. The sample is obtained by using a needle to draw off blood from veins into collection tubes and then immediately transported to the local laboratory. Blood samples will be stored until all analyses are completed. Safety laboratory results will be evaluated by the subinvestigator.

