### 9.7.2 *Laboratory assessments*

#### **Lipid assessment**

Sample collection will take place at each investigator site by the subinvestigator. The sample is obtained by using a needle to draw off blood from veins into collection tubes and then immediately transported to the local laboratory. Blood samples will be stored until all analyses are completed.

- High-density lipoprotein (HDL)
- Low-density lipoprotein (LDL)
- Total cholesterol

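### Section 11.1 makes hyperbilirubinemia and elevated TSH mandatory stops, but the protocol schedules no on-treatment test for either

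*Combined protocol and SAP*

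**What the plan says.** Section 11.1 allows the investigator to withdraw a participant for any adverse event, laboratory abnormality or condition that makes continuing against that person's interest. It then names findings for which immediate discontinuation is mandatory. One is "hyperbilirubinemia or jaundice", placed among the clinical events. A separate sub-list, introduced as "clinically significant laboratory abnormalities such as", contains four laboratory stops: creatine kinase (CK) above 5 times ULN, GOT or GPT above 3 times ULN, severe symptomatic hyponatremia, and "elevated thyroid-stimulating hormone outside of the age- and sex-specific reference intervals". No limit is given for bilirubin.

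The measurement schedule is in section 9.6.2: "Safety laboratory will be performed at screening, baseline, visit 4, visit 5 and at the end-of-study". The chemistry entry reads "Clinical chemistry [sodium, potassium, creatinine, estimated GFR, GOT (AST), GPT (ALT), gamma-GT", and the list then moves on to CK, CRP, glucose, HbA1c and beta-HCG. TSH has its own sentence: "At screening visit thyroid-stimulating hormone (TSH) and Carbohydrate-deficient Transferrin (CDT) will be additionally determined". The lipid panel (9.7.2) holds HDL, LDL and total cholesterol. The immunometabolism panel (9.7.2, selected sites only) holds cell function, gene expression, phenotyping and cytokines. Table 3 and the visit lists in 9.4 add neither bilirubin nor TSH after randomization.

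**The concern.** A mandatory stop that depends on a laboratory value needs either a scheduled measurement or a statement that it relies on clinical detection. Here the protocol gives neither for these two analytes.

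The TSH stop is the clearer case. Section 6.2.1 already bars patients with elevated TSH, and Table 3 checks inclusion criteria only at baseline. Apart from correcting an entry error, the stop can therefore act only after randomization, when no TSH is scheduled. The rule has a purpose: section 4.2.4 names subclinical hypothyroidism among the risk factors for statin myopathy, and a subclinical condition may give no clinical prompt for a test.

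For bilirubin, section 7.2.5 lists hepatitis/icterus and liver failure among simvastatin reactions, and hepatitis among those of escitalopram. Without a scheduled test, the stop depends on visible jaundice or on someone ordering the test. Section 9.6.1 places physical examinations at screening and end-of-study only, so none is scheduled while stopping could still alter treatment. What is at stake is timely action for an individual patient.

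**Working it through.** No statistical figure bears on this point. The check matches each measurable stop in 11.1 to a scheduled measurement after the first dose.

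| Stop in 11.1 | Scheduled on treatment | Source |
|---|---|---|
| CK | weeks 4, 8, 12 | 9.6.2 |
| GOT/GPT | weeks 4, 8, 12 | 9.6.2 |
| Sodium | weeks 4, 8, 12 | 9.6.2 |
| QTc | every visit | 9.6.3 |
| MADRS item 10 | every visit | 9.5.1 |
| CGI-I, two successive visits | visits 2 to 6 | 9.7.3 |
| Pregnancy | weeks 4, 8, 12 | 6.2.3 |
| TSH | none (screening only) | 9.6.2 |
| Bilirubin | none named | 9.6.2, 9.7.2, Table 3 |

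Counting the safety draws:

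- Total draws: 5. After the first dose: 5 − 2 (screening, baseline) = 3.
- Draws that can still change study treatment: 3 − 1 = 2 (weeks 4 and 8), because section 11.3 ends simvastatin after the last visit whatever the result.
- Draws listing bilirubin: 0 of 3 on treatment, 0 of 5 overall.
- Draws listing TSH: 0 of 3 on treatment, 1 of 5 overall.

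The count of three follows 9.6.2, Table 3 and section 10. Section 7.2.5 and the matching risk paragraph of the synopsis omit week 8. On that schedule the result is 0 of 2 for each analyte, with one draw still actionable.

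The other measurable stops each have a scheduled on-treatment test. TSH is the only one of the four named laboratory stops without one. That pattern suggests an oversight, although the documents do not say so.

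**The case against.** The strongest reply is that a stop list is not a monitoring schedule. Section 11.1 also mandates stopping for seizures, serotonin syndrome, interstitial lung disease and angle closure glaucoma, none of which has a dedicated scheduled test; such rules apply once a finding is known. This has force for bilirubin, which sits among the clinical events and is paired with jaundice. It has less force for TSH, which is listed as a laboratory value and has no clinical counterpart in the rule.

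A reader might infer that the two stops cannot operate, or that no on-treatment draw could lead to either. The documents do not support that. An abnormal GOT, GPT or gamma-GT must be assessed for clinical relevance (12.4), management of an event may include different or more frequent assessments (12.2), and an outside result would count. Dark urine is asked about at each visit (section 10), though as a sign of rhabdomyolysis.

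A reader might also take it as certain that bilirubin is absent from the panel. Section 9.6.2 says the components include the listed tests, and the chemistry bracket is not closed in the available text, so a lost analyte cannot be fully excluded. No other place names a bilirubin test. This doubt does not reach TSH, whose own sentence ties it to screening.

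On size, section 7.2.5 classes simvastatin hepatitis/icterus as rare, below 1/1,000. That means fewer than 80 × 0.001 = 0.08 expected cases in 80 simvastatin patients, or 120 × 0.001 = 0.12 in 120. The figure covers the reported reaction, not silent bilirubin rises, and escitalopram hepatitis has no stated frequency. It does support calling the gap small. Neither reaction list names a thyroid effect, and myopathy is covered by scheduled CK, its own stop and a muscle-symptom question at each visit.

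**Conclusion.** The point holds as a minor gap in scheduled monitoring. Two mandatory stops have no scheduled on-treatment test. For TSH the text is unambiguous; for bilirubin it is subject to the open bracket and the non-exhaustive wording.

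What scheduled tests leave uncovered is a bilirubin rise without visible jaundice or a relevant GOT, GPT or gamma-GT change, and a TSH rise that nothing prompts anyone to test. The documents give no rate for either, so no number of missed cases is claimed. The laboratory sub-list is open-ended and investigators may withdraw a patient for any worrying abnormality, which limits the consequence further. The primary analysis is not affected.

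**What to change.** In section 9.6.2, add total bilirubin to the clinical chemistry list at the existing baseline, week 4, week 8 and week 12 draws, and add TSH to one draw that can still change treatment, week 4 or week 8. In section 11.1, define the bilirubin stop relative to the local ULN and the patient's baseline value, so that a stable pre-existing elevation does not force discontinuation. The exact limit is a clinical choice for the sponsor.

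Upper bounds on cost, assuming every patient attends every draw:

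- Bilirubin: 4 × 160 = 640 assays; at the 240-patient cap in section 16.6, 4 × 240 = 960.
- TSH: 1 × 160 = 160 assays; at the cap, 240.
- Together: 640 + 160 = 800; at the cap, 960 + 240 = 1,200.

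If the 20% dropout in section 16.2 all fell before week 4 (an assumption about timing) and those patients had no further draws, bilirubin would need 160 + 3 × 128 = 544 assays and TSH 128, or 672 in total.

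No new visit or blood draw is needed. A few extra treatment discontinuations are possible; section 11.1 still follows those patients for safety and efficacy to week 12. Narrowing the bilirubin rule to jaundice or enzyme-linked rises, or deleting the TSH stop, would remove the mismatch on paper but weaken the protection, and is not recommended.
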